8.2.2. Definition of Flare

A flare is defined as a combination of an increase in DAS28-CRP of 1.2 units, or 0.6 if DAS28-CRP \geq 3.2, AND at least 2 swollen joints on examination of 44 joints (39, 40, 53).

If a participant does not fulfil the formal definition, but experiences a clinically significant worsening, according to both the investigator and participant, that leads to a major change* in treatment, this should be considered as a flare but be recorded separately in the eCRF.

*A major change in treatment includes:

- Switching to another bDMARD or a tsDMARD
- Adding a csDMARD
- Increasing the dose of a concomitant csDMARD
- Adding or increasing systemic glucocorticoids (per orally, intravenous or intramuscular)
- Receiving more than one intra-articular glucocorticoid injection at one visit
- Shortening the interval of the SC TNFi for clinical reasons (Standard of care group)

8.3. Safety Assessment

Safety will be monitored by laboratory tests (Section 8.3.1) and the collection of AEs at every onsite visit. Significant findings that are present prior to the signing of informed consent must be included in the relevant medical history/current medical condition page of the eCRF. For details on AE collection and reporting, see Appendix 3.

Any AE encountered during the clinical study will be reported in the eCRF (see Appendix 3 for definitions). AE will be followed up as clinically indicated until they have returned to

baseline status or are stabilized. Events which are definitely due to disease progression will not be reported as an AE/SAE.

- See Appendix 2 for the list of clinical laboratory tests to be performed and the SoA (Section 1.3) for the timing and frequency.
- The investigator must review the laboratory results, document this review, and record any clinically significant changes occurring during the study as an AE. The laboratory results must be retained with source documents.
- All laboratory tests with values considered clinically significantly abnormal during participation in the study or within 8 weeks after the last dose of study intervention should be repeated until the values return to normal or baseline or are no longer considered clinically significant by the investigator or medical monitor.
 - If clinically significant values do not return to normal/baseline within a period of time judged reasonable by the investigator, the etiology should be identified, and the sponsor notified.
 - All protocol-required laboratory tests, as defined in Appendix 2, must be conducted in accordance with the laboratory manual and the SoA (Section 1.3).
 - If laboratory values from non-protocol-specified laboratory tests performed at the institution's local laboratory require a change in participant management or are considered clinically significant by the investigator (e.g., SAE or AE or dose modification), then the results must be recorded.

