Endpoints	
Primary endpoint: Sustained disease control over the follow-up period of 18 months without flare, with flare defined as either of the following:
 
 • A combination of an increase in Disease Activity Score using 28 joints C-reactive protein (DAS28-CRP) > 1.2, or > 0.6 if DAS28-CRP ≥ 3.2, AND ≥ 2 swollen joints on examination of 44 joints

	
 • Consensus between patient and physician that a disease flare has occurred, leading to a major change in treatment 
If more than one TNFi type are included, subgroup analyses according to each TNFi type used will be performed.
 
Secondary endpoints:
 
 • Disease activity at 4, 8, 12, and 18 months assessed by DAS28-CRP, Evaluators Global Assessment of Disease Activity (EGA), Clinical Disease Activity Index (CDAI), Simple Disease Activity Index (SDAI), American College of Rheumatology (ACR)/European Alliance of Associations for Rheumatology (EULAR) remission criteria, Rheumatoid Arthritis Impact of Disease (RAID), Modified Health Assessment Questionnaire (MHAQ), biochemical parameters • Time to disease flare • Number and type of adverse events (AEs) • Drug survival, drug consumption, occurrence of ADAbs, serum drug levels
Overall Design	
A multicenter, randomized, two-arm, parallel-group, open, superiority trial where adult participants with RA in DAS28-CRP remission or low disease activity (DAS28-CRP < 3.2) on therapy with standard dose of a SC TNFi (adalimumab) for 3-24 months with indication for continuation of treatment according to the treating physician are stratified by country and allocated 1:1 to:
 
 • Administration of TNFi based on proactive TDM (TDM group) • Administration of TNFi based on standard of care without knowledge of serum drug levels or ADAbs status (Standard of care group) 
The protocol has been developed with the aim of including RA patients on therapy with adalimumab. If sufficient evidence emerges regarding therapeutic ranges of other SC TNFi during the study period, it will be considered to amend the protocol to include RA patients on other SC TNFi.

Visit Frequency	Onsite visits will be conducted at 0, 4, 8, 12, and 18 months following randomization, with additional digital visits and blood sampling at 2, 6, 10, 14, and 16 months.
Study Duration	18 months
Number of Participants	A minimum of 350 patients will be enrolled.

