1.3. Schedule of Activities (SoA)

Procedure	Screening	Intervention Period (visit month/visit no)										E/D	Extra Visit	Notes
		Baseline*	2	4*	6	8*	10	12*	14	16	18*			
		Visit 1	Visit 2	Visit 3	Visit 4	Visit 5	Visit 6	Visit 7	Visit 8	Visit 9	Visit 10			
Informed consent	X													
Inclusion and exclusion criteria	X	X												See Sections 5.1 and 5.2
Randomization		X												See Sections 6.3 and 9.3.1
Demography		X												See Section 8.1.1
Height and weight		X												See Section 8.1.1
Medical history including tobacco use		X												See Section 8.1.1
Current medical conditions		X												See Section 8.1.1
Routine laboratory tests		X		X		X		X			X	X	X	Hemoglobin, platelet count, white blood cells with differentials, ALT, creatinine, CRP, ESR. See Section 8.3.1
Biobank full blood		X												All sites See Section 8.1.2
Biobank**		X		X		X		X			X	X	X	Full blood, plasma and serum See Section 8.1.2
Assessment of disease activity		X		X		X		X			X	X	X	DAS28-CRP, EGA, 44 joint count, CDAI, SDAI See Section 8.2.1
Assessment of drug levels and ADAb***		X	X	X	X	X	X	X	X	X	X	X	X	See Section 8.5

RA-FQ, EQ-5D, WPAI:RA		X	X	X	X	X	X	X	X	X	X	X	X	X	See Sections 8.2.1 and 8.8
SF-36, MHAQ, RAID		X		X		X		X		X	X	X	X	X	See Sections 8.2.1 and 8.8
Record of concomitant medication for RA		X		X		X		X		X	X	X	X	X	See Section 6.9.2
AE registration		X		X		X		X		X	X	X	X	X	See Section 10.3
Adherence		X	X	X	X	X	X	X	X	X	X	X	X	X	By questionnaires and digital calendar See Section 6.5
	
*Onsite hospital visits ** Participants at Diakonhjemmet Hospital only ***In all participants AE = Adverse Events; ALT=Alanine Transaminase; E/D = Early Discontinuation; EGA = Evaluators Global assessment of disease activity; ESR= Erythrocyte sedimentation rate; EQ-5D = European Quality of Life 5 Dimensions; Ex visits = Extra visit if flare; CDAI = Clinical disease activity index; CRP= C-reactive protein; DAS28-CRP = Disease Activity Score using 28 joints C-reactive protein; MHAQ = Modified Health Assessment Questionnaire; PGA = Patient Global assessment of disease activity; RAID = Rheumatoid Arthritis Impact of Disease; RA-FQ = Rheumatoid Arthritis Flare Questionnaire; SDAI = Simple disease activity index; SF-36= 36-Item Short-form health survey; WPAI:RA = Work Productivity and Activity Impairment Questionnaire: Rheumatoid Arthritis
														

2. Introduction

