4.1. Overall Design

- A multi-center, randomized, open (with partial blinding for outcome assessments), parallel-group, superiority study.
- Study intervention assignment: 1:1 by central computer randomization at the time of inclusion, stratified by country.
- Treatment strategies compared:
 - Administration of TNFi based on proactive TDM (TDM group)
 - Administration of TNFi according to standard of care without knowledge of serum drug levels or ADAb status (Standard of care group)
- Population: Adult patients with RA in DAS28-CRP remission or low disease activity (DAS28-CRP < 3.2) on therapy with a SC TNFi (adalimumab) in standard dose for 3–24 months and an indication for continuation of treatment according to the treating physician.
- Algorithm for dose adjustments: In the TDM group, adjustments of the dosing interval of the TNFi are made according to a predefined algorithm, with the aim of reaching and maintaining a serum drug level within the therapeutic range.
- Duration of study: The randomized treatment strategy will be continued for the duration of the follow-up period (18 months).
- Study visits: Onsite visits 0, 4, 8, 12, and 18 months. Additional digital visits and onsite blood sampling at 2, 6, 10, 14, and 16 months.
- Primary endpoint: sustained disease control without disease flare during the follow-up period of 18 months.
 - In order to identify the primary endpoint, each study center will have a phone number for participants to call in case of increased disease activity. If a participant is experiencing a potential flare, a visit will be arranged within one week after contacting the study center to allow for a thorough examination and documentation of disease status.
- Participants experiencing a flare (primary endpoint) will be followed according to the visit scheme. Further therapy will be at the discretion of the treating physician, but for participants in the TDM group, an increase in dose will be recommended if the drug level is low (according to the TDM algorithm).
- Participants who are switched to another treatment during the study will still be followed according to the visit scheme but without TDM.
- Biosimilars: Switching between biosimilar drugs is allowed at any time during the study.

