6.1. Study Intervention Administered

6.1.1. The TDM Group

In the TDM, the SC TNFi dose will be adjusted according to the algorithms outlined in Table 1 in order to keep the drug level within the therapeutic range.

Prior to a dose change, the study personnel must check by a phone call to the participant if the drug has been administered according to the treatment algorithm (as defined in Table 1) or if injections have been postponed or dropped due to medical or other reasons.

The following exceptions from the algorithm in Table 1 are recommended if the drug has not been administered according to the treatment algorithm during the last month:

- If the drug level is low with no or low ADAb and there has been a pause in medication of more than 1 week for the last month prior to the blood sampling the dose should be kept stable
- If the drug level is high and the participant has taken the injection in a higher dose or more frequent than prescribed, the dose should be kept stable.

The reason for pause in therapy should be recorded in the eCRF.

In the TDM group, results for drug levels and ADAb will be reported to the investigators via the eCRF within 10 days after receiving the sample. Results in the standard care group will be recorded in the eCRF but not accessible to study personnel, and transferred to the PI upon conclusion of the clinical trial.

Table 1. Study Intervention

	Adalimumab	x	y	z
Trade name(s)	Originator and all approved adalimumab biosimilars*			
Type	Biologic drug			
Dose Formulation	Subcutaneous (SC) injection			
Recommended Dose**	40 mg SC every 14 days, if necessary 40 mg SC every 7 days or 80 mg SC every 14 days			
IMP and NIMP	IMP			
Drug target range	5.0-12.0 mg/L			
Cut-off ADAb high levels	> 50 µg/L			
TDM strategy				
• Within target range	Keep dose			
• Low drug levels, ADAb undetectable or low levels	Decrease dosing interval by one week to a maximum of 40 mg/week			
• Low drug levels, ADAb high levels	Switch to another therapy			
• High drug levels	Increase dosing interval by one week up to a maximum of 6 weeks			

* All adalimumab biosimilars approved by the European Medicines Agency
**According to the Summary of Product Characteristics (SmPC)
ADAb = anti-drug antibodies; TDM = Therapeutic drug monitoring

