8.4.3. Follow-up of AEs and SAEs

After the initial AE/SAE report, the investigator is required to proactively follow each participant at subsequent visits/contacts. All SAEs will be followed until resolution, stabilization, the event is otherwise explained, or the participant is lost to follow-up (as defined in Section 7.3). Further information on follow-up procedures is provided in Appendix 3.

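### Adverse event (AE) ascertainment can differ between arms: scheduled enquiry is the same, but only TDM participants get staff calls about medical reasons for missed injections

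*Protocol*

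**What the plan says.** **Scheduled AE enquiry.** Protocol Section 8.3 says: "Safety will be monitored by laboratory tests (Section 8.3.1) and the collection of AEs at every onsite visit". The Synopsis fixes the timing: "Onsite visits will be conducted at 0, 4, 8, 12, and 18 months following randomization". The AE row of the Schedule of Activities (SoA, Section 1.3) also covers early-discontinuation visits and extra visits, the latter explained as "Ex visits = Extra visit if flare".

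**Contacts between onsite visits.** Section 4.1 adds: "Additional digital visits and onsite blood sampling at 2, 6, 10, 14, and 16 months". Section 6.5 has both arms complete an injection calendar and a compliance questionnaire at these contacts. Section 8.3 does not place AE collection there.

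**Calls in the TDM arm.** Section 6.1.1 states: "Prior to a dose change, the study personnel must check by a phone call to the participant". The call covers whether the drug was taken as the algorithm requires, or "if injections have been postponed or dropped due to medical or other reasons". Section 6.5 repeats the call for dose adjustments under the protocol, with a four-week look-back, and has deviations recorded with their reasons. Standard-of-care doses are not adjusted by the algorithm, so in effect the call exists in one arm only.

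**Duty to report.** Section 8.3 also states: "Any AE encountered during the clinical study will be reported in the eCRF". Section 8.4 includes events that the participant reports.

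**The concern.** The trial is open-label and only the joint assessor is blinded. Staff who know the allocation make additional, unplanned contacts with one arm and ask a directed question about medical reasons for missed doses. Infections and similar illnesses are natural answers. The reporting duty does not depend on why staff phoned, so such an event has to be entered if it meets the AE definition. Section 8.4.2 promises care not to bias AE detection and prefers open, non-leading questions. A directed question put to one arm sits uneasily with that.

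AE number and type is the only safety endpoint (Section 3), and Section 2.3.2 names fewer adverse effects as a possible gain from TDM. The comparison is descriptive, with confidence intervals where appropriate (Section 9.1.1), and an interval does not reflect unequal ascertainment. Non-serious events, which are easily forgotten over 4 to 6 months, are the most exposed. Events that were never asked about cannot be recovered by a later analysis plan.

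**Working it through.** The plan gives no figure for AE ascertainment, so there is none to reproduce. The check has four steps.

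**1. Recall windows.** Onsite months 0, 4, 8, 12, 18 give gaps of 4, 4, 4 and 6 months. Of 10 scheduled contacts, 5 are onsite and 5 digital. The SoA columns are misaligned in the text available, so I rely on Section 8.3 for the AE schedule and not on exact SoA columns.

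**2. Opportunities for a call.** Samples at months 0, 2, 4, 6, 8, 10, 12, 14 and 16 can each lead to a dose change, which makes 9. Four (months 0, 4, 8, 12) are drawn at onsite visits where AEs are asked about anyway; five fall between enquiries. Samples should reach the laboratory within 7 days and results follow within 10 days of receipt: 7 + 10 = 17 days. If both targets are met and the call is made when the result arrives, at least 28 - 17 = 11 days of the four-week look-back were already covered by the onsite visit. Calls after digital contacts therefore add most. The number of calls is unknown: Section 2.2.2 says only that a substantial share of patients on standard dose lie outside the range, and some out-of-range results lead to a switch or are already at an interval limit (Table 1).

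**3. Illustrative size of the call effect.** Let
- b = share of AEs captured by the routes common to both arms,
- f = share of TDM-arm AEs in a window covered by a call,
- g = probability that the call surfaces an AE otherwise missed.

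With equal true rates, the TDM/control ratio of reported AEs is [b + f·g·(1 - b)]/b = 1 + f·g·(1 - b)/b. All three inputs are assumptions: b 0.6 to 0.9, f 0.05 to 0.4, g 0 to 0.5.

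| b | f | g | Ratio |
|---|---|---|---|
| any | any | 0 | 1.00 |
| 0.6 | 0.2 | 0.3 | 1 + 0.06 × 0.4/0.6 = 1.04 |
| 0.6 | 0.4 | 0.5 | 1 + 0.20 × 0.4/0.6 = 1.13 |
| 0.8 | 0.4 | 0.5 | 1 + 0.20 × 0.2/0.8 = 1.05 |
| 0.9 | 0.4 | 0.5 | 1 + 0.20 × 0.1/0.9 = 1.02 |

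**4. The opposing route.** Section 9.5 assumes 72.5% flare-free in control and 85% under TDM, so 27.5% - 15% = 12.5 percentage points more control participants have a flare. At the stated hazards, expected flares over 18 months differ by (0.0006 - 0.0003) × 365 × 1.5 = 0.16 per person. A flare visit carries formal AE registration. If a call surfaced AEs as well as a visit, 0.125/9 to 0.16/9, or about 1.4 to 1.8% of samples leading to a call, would offset this. If it did so only one-tenth as well (an assumption), the share would be 14 to 18%. Suspected flares that are not confirmed add visits in either arm and are not counted. The documents do not show which side of this balance the trial will fall on.

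**The case against.** The strongest reply is that planned AE elicitation is the same in both arms: same visits, same open-ended questioning. The call is an adherence check, not an AE enquiry. Both arms complete the two-monthly calendar and questionnaire, and Section 6.6 has the reason for a delayed dose, such as infection or surgery, recorded without restriction to one arm. An illness that interrupts dosing can therefore surface in control as well. Both arms also have the flare telephone line, with a visit within one week. The endpoint is secondary and descriptive, and the drug is a marketed one that participants already take.

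Most of this stands, and it limits the point. It does not remove it: the digital contacts carry no AE question, and no staff conversation is required there, whereas the TDM call is a conversation whose content is reportable.

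A reader might infer that AEs are collected only at onsite visits, or that detection is higher in the TDM arm by design. The documents do not support either. AEs are also registered at early-discontinuation and extra visits, and any AE encountered is reportable in both arms. Higher detection under TDM is possible, but more flare visits in control could offset or reverse it. A reader might also take Section 8.4.3, where "the investigator is required to proactively follow each participant at subsequent visits/contacts", as showing that calls detect new events. That sentence concerns follow-up after an initial report, in both arms.

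On the remedy, an electronic question departs from the verbal questioning preferred in Section 8.4.2, and the TDM calls would remain. Verbal follow-up of positive answers meets the first objection; recording the source of each AE addresses the second.

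**Conclusion.** The point holds as a potential for differential AE ascertainment. The contact asymmetry and the duty to report what it reveals are both in the text. The direction and size of any resulting bias are not. The illustrative range for the calls alone is 1.00 to 1.13, at most 1.05 if the common routes already capture 80% of AEs. It rests wholly on assumed inputs and leaves out flare visits. Enquiry every 4 to 6 months, equal in both arms, is a design choice and not an error in itself. This is a worthwhile, inexpensive improvement to a secondary endpoint; it does not affect the primary analysis.

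**What to change.** 1. In Section 8.3 and the SoA, add one open AE question, worded identically for both arms, to the existing digital contacts at months 2, 6, 10, 14 and 16, with verbal follow-up by the site of any positive answer. Scheduled gaps then become two months throughout.
2. Add an eCRF field for the contact at which each AE was first learned of: scheduled enquiry, dose-change call or extra visit.
3. Repeat the AE comparison using scheduled enquiries only, beside the comparison of all AEs. The restricted version drops some events that a later scheduled enquiry would have found, so the two should be read together.

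The cost is one form item, one eCRF field and a wording change, with no new visit and no change to any dosing or treatment rule. The downside is somewhat more non-serious AEs for sites to follow up in both arms.

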8.3.1. Routine Laboratory Tests

The following laboratory tests will be recorded at all visits. These tests will be analyzed at the local laboratory according to hospital procedures. If any requested tests are not available locally, samples will be referred to other laboratories according to local practice.

- Hematology: Hemoglobin, white blood cells with differentials and platelet count
- Blood chemistry: ALT, creatinine, ESR, CRP

8.4. Adverse Events (AEs) Serious Adverse Events (SAEs), and Other Safety Reporting

The definitions of AEs and SAEs can be found in Appendix 3.

The investigator and any qualified designees are responsible for detecting, documenting, and recording events that meet the definition of an AE or SAE and remain responsible for following up AEs that are serious, considered related to the study intervention or study procedures, or that caused the participant to discontinue the study intervention (see Section 7). This includes events reported by the participant (or, when appropriate, by a caregiver, surrogate, or the participant's legally authorized representative).

The method of recording, evaluating, and assessing causality of AEs and SAEs and the procedures for completing and transmitting SAE reports are provided in Appendix 3.

8.4.1. Time Period and Frequency for Collecting AE and SAE Information

All AE and SAEs will be collected from the start to stop of study intervention.

All SAEs will be recorded and reported to the sponsor or designee immediately and under no circumstance should this exceed 24 hours after the investigator is made aware of the SAE, as indicated in Appendix 3. The investigator will submit any updated SAE data to the sponsor within 24 hours of it being available.

Investigators are not obligated to actively seek information on AEs or SAEs after conclusion of the study participation. However, if the investigator learns of any SAE, including a death, at any time after a participant has been discharged from the study, and the investigator considers the event to be reasonably related to the study intervention or study participation, the investigator must promptly notify the sponsor.

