5.5. Criteria for Temporarily Delaying

Not applicable.

6. Study Intervention and Concomitant Therapy

Study interventions are all pre-specified investigational and non-investigational medicinal products, medical devices, and other interventions (e.g., surgical and behavioral interventions) intended to be administered to the study participants during the study conduct.

Participants enrolled in the RA-DRUM trial are on therapy with SC TNFi.

They are randomized 1:1 to either:

- Administration of SC TNFi based on proactive TDM (TDM group)
- Administration of SC TNFi according to standard of care without knowledge of serum drug levels or ADAb status (Standard of care group)

If the participants are using prednisolone (≤ 7.5 mg prednisolone oral dose or equivalent) or concomitant csDMARD including methotrexate, sulfasalazine, hydroxychloroquine, or leflunomide in any dose this will be continued in an unchanged dose.

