6.1.3. Both Groups

In order to identify the primary endpoint, each study center will have a phone number for participants to call in case of increased disease activity. If a participant is experiencing a potential flare, a visit will be arranged within one week after contacting the study center to allow for a clinical examination and documentation of disease status.

Participants with a flare (primary endpoint) will be followed according to the visit scheme. Further therapy will be at the discretion of the treating physician, but for participants in the TDM group, an increase in dose will be recommended if the drug level is low (according to the TDM algorithm).

If SC TNFi is terminated due to any reason, the participant will still be included in the study and followed with study visits according to the planned visit schedule. The reason for termination of therapy should be recorded in the eCRF. If SC TNFi is terminated due to AE, the choice of treatment should be at the discretion of the investigator. Participants who are

switched to another treatment during the study will still be followed according to the visit scheme. Switching between biosimilar drugs is allowed at any time during the study.

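### Section 8.4.1 ties the end of AE and SAE collection to the stop of study intervention, which conflicts with Section 8.3 and the Schedule of Activities and, taken literally, could bias the safety comparison

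*Protocol*

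**What the plan says.** Section 8.4.1, which is headed as the rule on the AE time period, states: "All AE and SAEs will be collected from the start to stop of study intervention". Later in the same section the boundary is different: "Investigators are not obligated to actively seek information on AEs or SAEs after conclusion of the study participation".

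Section 8.3 sets no on-drug condition. It says "Safety will be monitored by laboratory tests (Section 8.3.1) and the collection of AEs at every onsite visit", and then "Any AE encountered during the clinical study will be reported in the eCRF". The Schedule of Activities has an AE registration row running from baseline to month 18, with the early discontinuation and extra visits also marked.

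Follow-up does not end with the drug. Section 6.1.3: "If SC TNFi is terminated due to any reason, the participant will still be included in the study and followed with study visits". Section 4.1: "Participants who are switched to another treatment during the study will still be followed according to the visit scheme but without TDM". Section 7.1 asks that participants who permanently discontinue study intervention remain in the study if at all possible, and names only the primary outcome as the reason.

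Section 9.2 analyses safety by randomised group in the full analysis set. The safety endpoint in Section 3 is the number and type of AEs.

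**The concern.** The section that a site would consult for the AE window closes it at an event that can precede the end of follow-up, while other sections keep it open. If sites follow different sections, they collect different data after a stop or switch, and events not recorded at the time may not be recoverable later. The sentence covers SAEs as well as AEs. The explicit late-SAE duty in 8.4.1 begins only after discharge from the study, so the interval between stopping and discharge depends on what other sections imply.

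The reasons for stopping differ by arm by design. Table 1 directs a switch for low drug level combined with high ADAb in the TDM group. In the standard of care group these results are hidden (Section 6.1.2), so no such switch can occur. Treatment changes after a flare can occur in both arms (Section 6.9.2). A window that closes at the stop or switch would therefore depend on the assigned strategy, and the as-randomised comparison of AE counts would not rest on equal observation.

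**Working it through.** **1. What study intervention means in the protocol**

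| Place | Use of the term |
|---|---|
| Section 6, opening | "Study interventions are all pre-specified investigational and non-investigational medicinal products", and the sentence goes on to include devices and other interventions |
| Section 6.3 | The thing assigned is TDM or standard of care: the strategy |
| Table 1 (6.1.1) | Titled as study intervention; contains both the drug and the TDM rules, including the switch |
| Section 4.1 | The randomised strategy runs for all 18 months, but switched participants continue without TDM |
| Section 7.1 | Can be permanently discontinued while the participant stays in the study |
| Section 8.3 | Has a last dose: the drug |
| Section 10.3.1 | An AE is defined by its timing relative to use of the intervention |

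No single sense fits every row.

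**2. What each sense does to the 8.4.1 window**

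- Drug: the window closes when adalimumab stops. It would also open before consent, since Section 5.1 requires 3 to 24 months of prior therapy.
- TDM as a procedure: it closes at a switch in the TDM group, with no equivalent stopping point in the control group.
- 18-month randomised strategy: it closes at month 18 and agrees with Section 8.3 and the Schedule of Activities.

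**3. Possible size under the drug reading**

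The protocol gives no figure for this point and no rate of stopping adalimumab. What follows is an illustration on assumed rates.

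Inputs: follow-up T = 365 × 1.5 = 547.5 days; flare hazards 0.0006 (standard of care) and 0.0003 (TDM) per day from Section 9.5. These rounded hazards give exp(−0.0006 × 547.5) = 72.0% and exp(−0.0003 × 547.5) = 84.9% flare-free, close to the 72.5% and 85% stated there.

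Assumptions: a share s of flares ends adalimumab, and a proportion a of the TDM group stops for ADAb over 18 months (0 to 20%). The stopping hazards are λ = 0.0006s in standard of care and λ = 0.0003s − ln(1 − a)/T in TDM.

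Share of follow-up inside the window: (1 − exp(−λT)) / (λT).

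Example, s = 1: standard of care λT = 0.3285, so coverage = 0.280/0.3285 = 85.2%. TDM with a = 0: λT = 0.16425, coverage 92.2%.

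| s | a | Standard of care | TDM | Ratio TDM/standard of care |
|---|---|---|---|---|
| 0 | 5% | 100% | 97.5% | 0.975 |
| 0 | 20% | 100% | 89.6% | 0.896 |
| 0.5 | 0% | 92.2% | 96.0% | 1.041 |
| 0.5 | 20% | 92.2% | 86.2% | 0.934 |
| 1 | 0% | 85.2% | 92.2% | 1.082 |
| 1 | 20% | 85.2% | 82.9% | 0.973 |

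The ratio falls on either side of 1. ADAb-driven switches shorten the TDM window; flare-driven stops shorten the control window more, because the protocol expects about twice the flare hazard there.

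**4. After reconciliation**

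With collection to the end of study participation in everyone, planned coverage is 18 months in both arms and the ratio is 1.00, apart from withdrawals.

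**The case against.** The strongest reply is that the protocol already collects AEs to month 18 and 8.4.1 is only loosely worded. Section 6 includes other interventions in its definition, Section 6.3 assigns participants to TDM or standard of care, and Table 1 places the ADAb-triggered switch inside the intervention. Section 4.1 runs the strategy for the full 18 months. The start in 8.4.1 makes little sense for a drug begun before entry. Section 8.3, the Schedule of Activities and the later sentence of 8.4.1 have no on-drug condition, so a site working from the visit schedule would record AEs after a switch.

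Much of this stands. A reader might infer from 8.4.1 that AE collection does end when adalimumab stops. The protocol as a whole does not support that: the strategy reading is available and the other sections favour it. A reader might also infer that the safety comparison would flatter TDM, because only that arm has ADAb-triggered switches. That does not follow either, since stops after flares could remove more control time.

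The reply does not remove the conflict. Sections 7.1 and 8.3 treat study intervention as something that can end before the study does, Section 10.3.1 could be taken to confirm that later events are out of scope, and the strategy reading is itself unsettled by Section 4.1 stopping TDM at a switch.

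**Conclusion.** The protocol contradicts itself on the AE and SAE window, and the conflict lies in the section meant to settle it. If 8.4.1 is followed literally as the drug or as TDM, the window ends at a post-randomisation event affected by the assigned strategy, and the as-randomised AE comparison could be biased. Neither size nor direction can be determined from the document. The range of about 0.90 to 1.08 in relative AE-observed time rests on assumed stopping rates, constant hazards and the drug reading; under the strategy reading there is no loss. This is a correctable wording conflict in the safety section. It does not touch the primary endpoint, its analysis or the sample size. It is worth correcting because safety is a stated secondary objective and missed events may not be retrievable.

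**What to change.** Reconcile 8.4.1 with Section 8.3 and the Schedule of Activities by replacing the sentence with a single window, for example: AEs and SAEs are collected in all randomised participants from randomisation to the 18-month or early discontinuation visit, whether or not adalimumab or TDM has stopped. This avoids relying on the term study intervention to set the window. It would help to add in Section 7.1 that participants who discontinue the intervention are followed for safety as well as for the primary outcome.

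The cost is one or two sentences in an amendment. The visits continue already, and AE registration is already in the Schedule of Activities, so no new visits or forms are needed.
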